## 2. Study Objectives

### 2.1 Study 1

Study 1 will test the central hypothesis that high dose isoflurane anesthesia inducing EEG burst suppression (High ISO/BS+) is a more effective intervention for severe depression when compared to a low dose isoflurane anesthesia that does not induce EEG burst suppression (Low ISO/BS-). The proposed study is a randomized, double-blind trial that will evaluate 30 actively depressed participants with moderate to severe depression. Depression outcomes will be compared between two groups of participants (n=15 per group) who have received 10 treatment applications over a period of three weeks of either High ISO/BS+ or Low ISO/BS-.

Aim 1. To determine whether High ISO/BS+ is more effective than Low ISO/BS- in producing either a treatment response (defined as 50% reduction in depression scores) or full remission of depressive symptoms. We hypothesize that significantly more depressed participants randomized to receive 10 treatments of High ISO/BS+ compared to Low ISO/BS- will show a positive treatment response or full remission by treatment end. Based on the STAR\*D Trial, a responder is a participant showing 50% reduction in depression score and full remission is defined as a score of 0-10 on the HRSD-24 scale and score of 0-5 on the QIDS-SR16.

Aim 2. Preliminary data on neural and immune pathways that are differentially affected by the 2 treatments and associated with antidepressant effects will be explored by comparing changes from pre-treatment to post-treatment in full transcriptome leukocyte gene expression (using the RNA Seq method).

Aim 3. To measure the central neurochemical effects of isoflurane treatment, we will quantify neurotransmitter levels (GABA and glutamate) using magnetic resonance spectroscopy.

### 2.2 Pilot Study 2

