## **5.3 Clinical Assessments**

**5.3.1 Primary Response Assessments:** The primary outcome measure is change in depressive symptoms assessed by the Hamilton Rating Scale for Depression (HRSD-24), which is the most widely used method of evaluating the effectiveness of treatments to relieve depression. HRSD-24 will be administered as part of a clinical interview by blinded investigators prior to beginning the treatments, then repeated before treatment #6 and at the end of treatments.

**5.3.2 Secondary Response Assessments to be acquired before each treatment:** Also as standard of care for patients receiving ECT, the participant will fill out the Quick Inventory of Depressive Symptomatology (QIDS-SR) which is a patient self-report measure of depressive symptoms prior to each treatment session. QIDS scores will also be used as a safety measure. If 2 consecutive QIDS scores indicate worsening of depressive symptoms, below pre-treatment values, the study participant will meet with one of the study Psychiatrists to discuss treatment alternatives. The Montreal Cognitive Assessment (MoCA), Generalized Anxiety Disorder scale (GAD-7), and Work and Social Adjustment Scale (WSAS) will be administered prior to beginning the treatments, then repeated before treatment #6, and 48-72 hours post treatment #10.

**5.3.3 Follow-up Assessments to be acquired monthly for up to 6-months post treatment period:** Follow-up assessments will include QIDS-SR, WSAS, and an opened ended question about the participant's experience during the study. Follow-up assessments will be administered over the phone or by email with a link to an electronic survey housed on REDCap (a secure online database). A voicemail may be left (with prior permission) regarding the follow-up assessments.

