### **6.3 Safety and Efficacy Monitoring**

All serious adverse events will be reported within 5 days to the Data and Safety Monitoring Board (DSMB) and IRB by the Principal Investigator or study coordinators. These would include life-threatening cardiac arrhythmias, respiratory arrest, myocardial infarction, stroke, and death. Moderate adverse events including worsening of depressive symptoms will be reported to the DSMB. An interim data analysis will be performed at the midpoint of this pilot investigation, after data is obtained from 5 participants in each of the treatment conditions. The study will be terminated if significantly greater negative outcomes are associated with either isoflurane treatment or propofol treatment.

Prior to each treatment, participants will fill out the QIDS-SR. HRSD-24 will be obtained at baseline, before treatment 6, and after treatment 10. All participants will be assessed before the 6th treatment. If participants in Low ISO/BS- or propofol treatment groups show clinical deterioration (defined by 2 consecutive QIDS scores below baseline OR a decrease in HRSD-24 before the 6th treatment), they will be offered treatment at the 80% burst suppression level (High ISO/BS+) as it has proven effective in reducing depression or ECT as the standard of care treatment. Participants in High ISO/BS+ treatment who show clinical deterioration, as defined above, will be offered ECT. All serious adverse events will be reported within 5 days to the DSMB by the Principal Investigator or study coordinators. The DSMB will also be notified within 10 business days if a study participant is showing signs of clinical deterioration (defined as 2 consecutive QIDS scores below baseline OR HRSD-24 below baseline). Progress reports will be submitted every 6 months. If a participant has a serious reaction to anesthesia, they will be withdrawn from the study.

As exploratory biomarkers, we will evaluate whether quantitative cortical EEG changes early in treatment (obtained from dual lead BIS data in each treatment session) are associated with subsequent remission in depressive symptoms.

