## **7. Statistical Considerations**

Statistical analyses will employ a statistical mediation model framework. Any participant missing necessary information will be excluded from statistical analysis. Only participants with usable data will be included in the analyses. If the original statistical plan becomes infeasible, the original plan and the modifications made will be reported.

**7.1 Aim 1.** To determine if significantly more depressed participants randomized to receive 10 treatments of High ISO/BS+ will show a positive treatment response (defined as 50% reduction in depression scores) or achieve full remission of symptoms by treatment end compared to those in the Low ISO/BS-group, odds of treatment response and remission will be compared between groups using logistic regression analysis with positive response at treatment end (yes/no) as the dependent variable, and treatment group (High ISO/BS+ vs Low ISO/BS-) as the independent variable. Positive treatment response is defined as 50% reduction in depression scores, and remission will be defined as a score of 0-10 on the HRSD-24 scale.

Covariates will include baseline depression severity and possibly other baseline demographic and clinical measures as needed.

**7.2 Aims 2 and 5.** Using RNA SEQ methods, we will also explore whether participants who respond to treatment show blood-based changes in gene expression of neural and immune pathways previously associated with refractory depression or suicidality by our group or others. A t-test or non-parametric Wilcoxon test will be used, as appropriate. Change from baseline to end of treatment in gene expression levels will be correlated with change from baseline to end of treatment in HRSD-24.

**7.3 Aim 4.** In the open-label trial of propofol, initial evidence of efficacy will be defined by the percent of participants who show at least a 20% reduction in both HRSD and QIDS scores (initial improvement, as employed in the STAR D investigation) and who are propofol/BS+ responders (defined as 50% or more reduction in both HRSD-24 and QIDS scores). Secondary evidence of efficacy will be defined by comparing the percent of participants who are responders to propofol/BS+ vs. to the Low ISO/BS- control condition in the randomized trial.

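### The exploratory EEG biomarker analysis names only yes/no remission as its outcome; relating EEG to the full HRSD-24 score would be a nearly free improvement, with a power gain that depends on assumptions the plan does not state

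*Combined protocol and SAP*

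**What the plan says.** The EEG objective is a single sentence at the end of section 6.3. It is labelled exploratory ("As exploratory biomarkers, we will evaluate whether quantitative cortical EEG changes early in treatment"), and the one outcome it names is remission: the question is whether those changes "are associated with subsequent remission in depressive symptoms". It names no test, model, significance level or covariates, and does not say whether the three treatment groups are pooled. Section 7 does not mention EEG.

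Remission is a yes/no classification, and it is defined in two ways:

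- Section 7.1: "remission will be defined as a score of 0-10 on the HRSD-24 scale".
- Section 2.1, Aim 1: "full remission is defined as a score of 0-10 on the HRSD-24 scale and score of 0-5 on the" QIDS-SR16, so both scales must be low.

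The uncut score is available. Section 6.3 says "HRSD-24 will be obtained at baseline, before treatment 6, and after treatment 10", and section 5.3.1 makes it the main scale of the trial: "The primary outcome measure is change in depressive symptoms assessed by the Hamilton Rating Scale for Depression (HRSD-24").

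For the other biomarker, section 7.2 uses the full scale: "Change from baseline to end of treatment in gene expression levels will be correlated with change from baseline to end of treatment in HRSD-24". Nothing equivalent is written for EEG.

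**The concern.** The EEG measure is quantitative and so is the HRSD-24, but the only association written down is with a threshold on the second.

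The threshold treats unlike outcomes as alike. Entry requires HRSD above 18 with no upper limit (section 4.1). On the HRSD-24-only definition, a participant who starts at 19 and ends at 10 has fallen 9 points and is a remitter. One who starts at 35 and ends at 15 has fallen 20 points and is classed with those who did not improve.

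The Background says objective markers that predict clinical improvement are greatly needed, and improvement is a matter of degree. With at most 40 participants, and fewer remitters, a yes/no outcome makes it easier to miss a moderate association that the collected data could show. A full-scale analysis chosen after the data are seen would also carry less weight than one written in advance.

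**Working it through.** The plan has no power figure for this objective, so there is none to reproduce. What follows estimates the loss under stated assumptions.

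**Inputs from the documents**

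- Group sizes 15, 15 and 10, total 40 (sections 5.1.1 and 5.1.2; the Background also counts 40). Section 4.3 gives a total of 45, which does not match its own 30 + 10; 40 is used here.
- Remission of 50% with High ISO/BS+, from the earlier open-label study of 8 patients (Background).
- Remission of 50% with propofol, the target in section 2.2.

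**Assumptions**

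- Low ISO/BS- remission 10%, 20% or 30%.
- Within-arm correlation r between EEG change and end HRSD-24 of 0.2 to 0.5.
- Two-sided 5% test.
- All participants analysable.

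**Hand check, ignoring arm.** Power for a correlation is approximately Φ(atanh(r)·√(n−3) − 1.960). Cutting a normal outcome at remission rate p multiplies r by φ(z_p)/√(p(1−p)), which is 0.798 at p = 50% and 0.759 at p = 30%. For n = 40 and r = 0.4:

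- Full score: 0.4236 × 6.083 − 1.960 = 0.617, power 73%.
- Cut at 50%: r becomes 0.319; 0.331 × 6.083 − 1.960 = 0.05, power 52%, a loss of 21 points.
- Cut at 30%: r becomes 0.304; 0.313 × 6.083 − 1.960 = −0.05, power 48%, a loss of 25 points.

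**Simulation with arm in both models.** The EEG predictor x is standard normal. The latent end score is r·x + √(1−r²)·e, shifted by arm to give that arm's remission rate. The full score is analysed by linear regression on arm and x (t-test of x). Remission is analysed by logistic regression on arm and x (likelihood-ratio test of x), dropping arms in which remission does not vary. There were 1,500 trials per scenario, with a Monte Carlo standard error of about 1.3 points or less. Each cell shows Low ISO/BS- remission of 10 / 20 / 30%:

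| r | Full score, power % | Remission, power % | Loss, points |
|---|---|---|---|
| 0.3 | 45.5 / 46.9 / 46.5 | 29.6 / 33.7 / 35.5 | 15.9 / 13.2 / 11.0 |
| 0.4 | 73.9 / 72.2 / 72.2 | 52.5 / 50.7 / 54.6 | 21.4 / 21.5 / 17.6 |
| 0.5 | 91.7 / 91.8 / 90.5 | 67.3 / 71.8 / 75.3 | 24.4 / 20.0 / 15.2 |

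Repeat runs with 3,000 trials put the range at about 10 to 24 points.

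**Smaller or weaker cases**

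- Study 1 only (n = 30, Low ISO/BS- remission 20%): about 10 to 22 points for r of 0.3 to 0.5. At r = 0.4 power is 60% against 41%.
- r = 0.2: about 5 points or less.
- One arm of 15 at about 50% remission: roughly 0 to 11 points.
- Losses are larger where remission is rarer.

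**Limits of the simulation.** With no true association, the linear test rejected in about 5% of trials and the logistic test in 6 to 7%, so the remission figures are slightly flattered. Baseline adjustment was not simulated; either model could carry it.

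**The case against.** **The analysis is not fixed as binary.** Section 6.3 names no test, so the logistic model above is only a comparator. This stands: a reader might infer that the plan commits to a logistic regression on remission, and it does not. But remission is the only outcome it names, so a full-scale analysis would not be prespecified.

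**The size is conditional.** A reader might quote a loss of 11 to 24 points as a property of the trial. The documents do not support that. They give no EEG effect size, alpha or pooling rule, and section 4 describes two separate studies, one randomized and one open-label. Forty is also a ceiling: section 7 excludes participants with missing information, and section 6.3 allows some to be offered another treatment. At an assumed 12/12/8 the gain at r = 0.3 is about 8 points. Burst suppression is titrated to an arm-specific level (80%, or at most 20%). If the EEG measure is based on it, its within-arm spread is restricted and correlations of 0.3 to 0.5 may be generous.

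**The EEG objective is not the only categorical one.** A reader might infer that it alone discards the score. Aims 1 and 4 are also analysed by category, and section 7.2 first frames gene expression around responders. The contrast that holds is narrower: the other biomarker also has a full-scale analysis.

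**Baseline severity.** A reader might infer that the planned analysis would mistake high starting severity for poor effect. Section 7.1 lists baseline severity as a covariate for Aim 1, and section 6.3 does not rule it out for EEG.

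**Remission is a legitimate target.** It is central to Aims 1 and 4, and asking whether EEG predicts it is reasonable. That argues for keeping it, but not for making it the only outcome.

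**Conclusion.** The point stands as a cheap improvement of modest priority. Section 6.3 names only remission for the EEG biomarker, while the full HRSD-24 is already collected and already used for gene expression.

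For correlations of 0.3 to 0.5, the yes/no outcome costs roughly 10 to 24 points of power with all 40 analysable, and about 10 to 22 in Study 1 alone. The cost is small at r = 0.2 and can be close to nothing in a single arm of 15. These figures rest on the assumed correlation, the assumed Low ISO/BS- remission rate, a two-sided 5% test, and arm in both models.

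Remission is purely a cut of the HRSD-24 only under section 7.1. Under section 2.1 it also needs a low QIDS-SR16, which cannot increase the number of remitters. No numbered aim is affected.

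**What to change.** Replace the outcome in the section 6.3 sentence with wording such as:

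> Early EEG change will be related to the end-of-treatment HRSD-24 score by linear regression adjusted for baseline HRSD-24 and treatment arm. The association with remission will also be reported.

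Before that, reconcile the remission definitions in section 2.1 (HRSD-24 and QIDS-SR16) and section 7.1 (HRSD-24 only), so that the reported association uses one definition. State also whether the model covers Study 1 only or all three groups.

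The cost is a sentence or two of analysis text, with no new data, visits or participants. The small downside is that the lead result is in HRSD-24 points rather than odds of remission.

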## **7. Statistical Considerations**

Statistical analyses will employ a statistical mediation model framework. Any participant missing necessary information will be excluded from statistical analysis. Only participants with usable data will be included in the analyses. If the original statistical plan becomes infeasible, the original plan and the modifications made will be reported.

**7.1 Aim 1.** To determine if significantly more depressed participants randomized to receive 10 treatments of High ISO/BS+ will show a positive treatment response (defined as 50% reduction in depression scores) or achieve full remission of symptoms by treatment end compared to those in the Low ISO/BS-group, odds of treatment response and remission will be compared between groups using logistic regression analysis with positive response at treatment end (yes/no) as the dependent variable, and treatment group (High ISO/BS+ vs Low ISO/BS-) as the independent variable. Positive treatment response is defined as 50% reduction in depression scores, and remission will be defined as a score of 0-10 on the HRSD-24 scale.

Covariates will include baseline depression severity and possibly other baseline demographic and clinical measures as needed.

**7.2 Aims 2 and 5.** Using RNA SEQ methods, we will also explore whether participants who respond to treatment show blood-based changes in gene expression of neural and immune pathways previously associated with refractory depression or suicidality by our group or others. A t-test or non-parametric Wilcoxon test will be used, as appropriate. Change from baseline to end of treatment in gene expression levels will be correlated with change from baseline to end of treatment in HRSD-24.

**7.3 Aim 4.** In the open-label trial of propofol, initial evidence of efficacy will be defined by the percent of participants who show at least a 20% reduction in both HRSD and QIDS scores (initial improvement, as employed in the STAR D investigation) and who are propofol/BS+ responders (defined as 50% or more reduction in both HRSD-24 and QIDS scores). Secondary evidence of efficacy will be defined by comparing the percent of participants who are responders to propofol/BS+ vs. to the Low ISO/BS- control condition in the randomized trial.

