### **Subject Withdrawal and Study Completion**

Subject compliance will be monitored throughout the trial by study staff. If any contraindications to the study are identified, participants may be withdrawn by the investigators. Participants can be withdrawn at any point if the investigators feel it is in the participant's best interest or in the interest of study integrity. No information will be collected from withdrawn participants unless it is related to a continuing AE or SAE.

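### Aim 1 drops participants with missing outcomes, stops efficacy data at withdrawal, and has no scoring rule for arm-specific rescue; outcome-related loss that differs by arm would bias the odds ratio

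*Combined protocol and SAP*

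**What the plan says.** Section 7 sets one rule for missing data: "Any participant missing necessary information will be excluded from statistical analysis. Only participants with usable data will be included in the analyses". It gives no imputation, no non-responder rule, no sensitivity analysis and no named analysis set. Section 7.1 then compares response and remission at treatment end by logistic regression on treatment group. It adds that "Covariates will include baseline depression severity".

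Under Subject Withdrawal and Study Completion, the plan states: "No information will be collected from withdrawn participants unless it is related to a continuing AE or SAE". Withdrawal itself is discretionary: "Participants can be withdrawn at any point if the investigators feel it is in the" interest of the participant or of the study's integrity.

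Section 6.3 offers rescue after clinical deterioration. For Low ISO/BS- and propofol participants, "they will be offered treatment at the 80% burst suppression level (High ISO/BS+) as it has proven effective in reducing depression", with ECT as the alternative. For the other arm, "Participants in High ISO/BS+ treatment who show clinical deterioration, as defined above, will be offered ECT".

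The Risks of Worsening Depression text in section 9.1 describes ECT and medication as treatments available after a participant has left the study. No section says how a Low participant who accepts High ISO/BS+ is analysed.

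Section 7.3 reuses the Low-arm response rate, "comparing the percent of participants who are responders to propofol/BS+ vs. to the Low ISO/BS- control condition in the randomized trial".

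**The concern.** Taken together, these rules can remove participants from Aim 1 because of how they are doing. A participant who deteriorates and takes ECT appears to leave the study. The final HRSD-24 is then not collected, and section 7 excludes the participant. A Low participant who accepts High ISO/BS+ is either excluded or scored in Low after receiving the experimental treatment; the plan does not say which.

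Rescue is triggered by depression scores, so a link to outcome is built in. If High ISO/BS+ works as hypothesised, more deterioration in Low is foreseeable. Excess loss of Low non-responders raises the apparent Low response rate and hides a true effect. Excess loss of High non-responders inflates the effect. With 15 per arm, a few participants matter, and a scoring rule chosen after the data are seen could decide the result. The propofol comparison in section 7.3 inherits any distortion of the Low-arm rate.

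A participant who stops treatment but still has a final HRSD-24 stays in the analysis. The problem is missing outcomes and unscored rescue, not stopping as such.

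**Working it through.** **Inputs from the documents.** 15 per arm (section 2.1); logistic regression (7.1); 75% response to High ISO/BS+ in the sponsor's open-label study of 8 patients (section 3). Section 4.5 bases the sample size on that study and gives no alpha, power, control rate or dropout allowance, so there is no planned power figure to reproduce.

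**Assumed inputs.** Low-arm response of 25% (effect present) or 40% in both arms (no effect); loss from 0 to 50%; two-sided 0.05. The plan names no test statistic, so likelihood-ratio (LR) results are given with Wald in brackets.

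**When bias arises.** In an arm with true response p, let a fraction r of responders and s of non-responders be retained. The complete-case odds are p·r / [(1−p)·s], so

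complete-case OR = true OR × (r_High/s_High) / (r_Low/s_Low).

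If loss is unrelated to outcome within each arm (r = s), the factor is 1 however unequal the loss rates are. It is also 1 if r/s is the same in both arms. Bias therefore needs outcome-related loss that differs by arm. In the extreme case where only non-responders are lost, at fraction f, the factor is (1−f_Low)/(1−f_High).

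**Size in that extreme case** (exact enumeration, unadjusted; Wald counted as non-significant under separation):

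| Non-responders lost, one arm | 75% vs 25%, lost from Low: OR | Power | 40% in both, lost from High: OR | Rejection |
|---|---|---|---|---|
| 0% | 9.0 | 81% [78%] | 1.00 | 4.9% [3.8%] |
| 10% | 8.1 | 77% [74%] | 1.11 | 5.6% [4.9%] |
| 20% | 7.2 | 71% [67%] | 1.25 | 6.6% [5.8%] |
| 30% | 6.3 | 63% [58%] | 1.43 | 8.2% [7.1%] |
| 50% | 4.5 | 43% [36%] | 2.00 | 14.9% [12.0%] |

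For example, at 30% the OR is 9 × 0.7 = 6.3, and the apparent Low response rate is 0.25/(0.25 + 0.75 × 0.7) = 32% instead of 25%. Losing 20% of non-responders in both arms leaves the OR at 9.0, with power 78% [71%].

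**With baseline severity as covariate** (10,000 simulated trials per cell, assumed log-odds −0.5 per SD, Monte Carlo SE at most 0.5 points), the pattern is the same. At 0/10/30% loss, LR power is 85/79/65% and LR rejection is 6.2/6.8/9.2%.

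**Crossovers scored in Low.** If 30% of Low non-responders cross over and half of them respond, apparent Low response is 0.25 + 0.75 × 0.3 × 0.5 = 36%. The OR is then 5.3 and power 58% [55%]. This is one possible reading; the plan does not adopt it.

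**Single trials, unadjusted p-values:**
- 11/15 High vs 4/15 Low: p = 0.009 [0.014]. Excluding two Low non-responders gives 0.022 [0.030], three 0.035 [0.044], four 0.058 [0.067].
- The same trial with two Low crossovers who both respond and are scored in Low (11/15 vs 6/15): 0.063 [0.072].
- 8/15 High vs 4/15 Low: 0.133 [0.142]. Excluding three High non-responders gives 0.035 [0.044].

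**The case against.** The strongest reply is that the size is assumed throughout. Treatment lasts three weeks, rescue requires deterioration (narrower than non-response), and at 10% loss power falls only from 81% to 77%. In the 11/15 versus 4/15 example, four of the 11 Low non-responders must be excluded before significance is lost. The loss table is also the extreme case in which no responder is lost. All of this stands, and it limits the weight of the point. It does not remove the defect, because the loss follows from rules the plan states.

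A reader might infer that any difference in dropout between arms biases Aim 1. It does not, as the general formula shows.

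A reader might also infer that all rescue is left undefined. The section 9.1 text suggests that participants who take ECT leave the study, so the open question is mainly the Low participant who accepts High ISO/BS+. In section 7.1, describing groups as randomised leans towards analysis as assigned, but does not settle how that participant's outcome is scored.

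An HRSD-24 before treatment 6 is already scheduled (sections 5.3.1 and 6.3), so HRSD-triggered rescue already has a pre-rescue score. Only QIDS-triggered rescue at another time may lack one.

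Finally, the trigger is worded as "2 consecutive QIDS scores below baseline OR a decrease in HRSD-24 before the" sixth treatment, which read literally would offer rescue to improving participants. Section 5.3.2 speaks of worsening, so the intent is clear. This is a separate wording correction and adds no weight here.

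**Conclusion.** The point holds and should be fixed. Following the plan as written can bias the Aim 1 odds ratio if loss or rescue is related to outcome to a different degree in each arm. The direction depends on which arm loses more non-responders. The plan's text makes excess rescue in Low the more foreseeable case, and losing those participants would weaken a true effect. The documents do not support saying that the trial will be biased, or that the plan favours High ISO/BS+.

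The size is unknown. Under the assumed response rates and the only-non-responders-lost case, the effect is small at about 10% loss or with equal loss, and material at about 30% or more in one arm.

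**What to change.** 1. **Subject Withdrawal.** For participants who stop study treatment or take rescue without withdrawing consent, still obtain the treatment-end HRSD-24 as scheduled. Where QIDS triggers rescue at a time other than treatment 6, obtain an HRSD-24 before rescue if possible.
2. **Section 7, Aim 1.** Replace the exclusion rule with: *All randomised Study 1 participants are analysed in their assigned arm; treatment end is the originally scheduled post-treatment visit. Participants who take rescue or have no treatment-end HRSD-24 are counted as non-responders.* Add two sensitivity analyses: observed treatment-end HRSD-24 as assigned, and Low crossovers counted as responders. Report complete case for comparison, and say whether the conclusion holds in all. Apply the same Low-arm rule in section 7.3.
3. **Section 6.3.** State that rescued participants stay in follow-up.

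The cost is wording, continued collection of an assessment already scheduled, and at most one extra HRSD-24 per rescued participant. Reported response rates will be slightly lower.

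The non-response rule is not automatically conservative. If only non-responders are lost or rescued, it recovers the full-data result exactly. If Low participants who would have responded also cross over, it favours High ISO/BS+. As a stress test, take 40% response in both arms and a fraction c of Low crossing over regardless of outcome, so that apparent Low response is 0.40 × (1−c). At c = 10/20/30/50%, rejection is 5.6/7.5/11.0/23.5% [4.1/5.2/7.1/13.2%]. Crossover independent of outcome is unlikely under a deterioration trigger, but this is why the two sensitivity analyses belong with the rule.
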